### 7.1.4 Last Study Visit

• At their last study visit, participants will complete questions addressing overall condom preference (the study outcome for Aim 2). These pairwise comparison questions will assess preference for (1) fitted or standard condoms, (2) thin or standard condoms, and (3) fitted or thin condoms. Questions specific to the last study visit are uploaded to eIRB.

#### 7.1.5 Reminders

- Participants will be instructed to complete a daily mobile-optimized, webbased home coital logs, and to complete a coital log entry as soon as possible after each study condom use.
- To assist participants in timely completion, participants will receive a daily email or text reminder with a link to the password-protected coital log if the participant has not completed a log in the last day
  - Participants will receive an initial reminder at the time of their choosing.
    - If the participant does not post a coital log entry within a specified time period after their initial reminder, they will receive a second reminder.
    - If the participant does not complete the daily coital log regularly, study staff will contact participants to encourage more consistent completion.
- Study staff will send participants appointment reminders using their preferred method of contact 3 days before, 1 day before, and the day of each study visit.
- If we find that participants have certain preferences regarding reminders, we may alter the frequency and method of reminders as needed.
- Example reminder scripts are uploaded to eIRB.

### 7.1.6 Coital Log

- Participants will be instructed to complete mobile-optimized, web-based home coital logs as soon as possible following any vaginal or anal sex acts.
  Participants can complete a coital log entry on a smartphone, tablet, or personal computer. For participants without access to web browsers at home, we will provide smartphones for their use during the study.
- The coital log will first ask whether the participant has had sex since their last coital log entry. If the participant has had sex, the coital log will explore event-level condom use factors including:
  - Sex event questions
    - o Date and time of day of condom use
    - Color of condom bag
    - o Partner name
    - Lubricant use
    - o Type of sex act
    - o Quality of erection
    - o Condom fit
    - o Drug or alcohol use by participant or partner
  - Outcomes (described below in 7.3.4. Outcome Measures)
    - Clinical condom performance:
      - For breakage, we will assess when the breakage occurred.

- For slippage, we will assess when the slippage occurred, whether they held onto the condom at the base of the penis while withdrawing, and whether the penis was still erect upon withdrawal.
- o Event-level sexual pleasure scale

#### 7.2 Referral Procedures

### 7.2.1 Laboratory Referrals

All participants who have a preliminary positive HIV rapid test result, two invalid results, or are unable to provide enough blood for the rapid test at the enrollment visit will be scheduled to receive confirmatory testing at a private location of Emory's choosing. Confirmatory testing will include the participant having blood drawn for 4th generation immunoassay with reflex confirmatory testing. Participants testing preliminary positive will also be given the option to sign an assent form that would allow us to share their results directly with providers upon linkage to care. Laboratory testing will be done at a Clinical Laboratory Improvement Amendments (CLIA)-certified study laboratory. Results will be sent directly to study staff.

All participants who have had unprotected anal sex with a man OR have injected a substance not prescribed to him in the past 30 days AND self-report symptoms of acute HIV infection at their enrollment or follow-up visits will have blood drawn for viral load testing. Laboratory testing will be done at a CLIA-certified study laboratory, with results sent directly to study staff.

#### 7.2.2 HIV Referrals

Once confirmatory results are received, study staff will contact the participant by phone. If the result is negative, the participant will be informed during the phone call. If the result is positive, the participant will be requested to come in for an additional visit, with the goal of having participants seen within 1-2 business days of their confirmed positive test result. Participants will be referred for individual assistance in accessing HIV care and treatment services at an appropriate organization experienced with HIV care such as AID Atlanta or Pride Medical in Atlanta, Georgia.

#### 7.2.3 STI Referrals

All participants who are symptomatic for STIs at their enrollment or follow-up visits will be referred to either AID Atlanta or Pride Medical. AID Atlanta offers free STI screening and treatment, and we have successfully referred more than 190 men for STI treatment in previous studies (NIH study number: R01HD067111, R01MH085600).

#### 7.2.4 Acute HIV Referrals

Once results are received, study staff will contact the participant by phone. Those with detectable viral load will be brought in for a visit, targeting within 24 hours of receiving a positive results. Participants at the visit will receive counseling regarding the infectiousness of the acute period, and the need to be particularly cautious. The

participants will be referred to appropriate care for acute infection. If participant has no detectable viral load, we will seek to reschedule their study visit to complete study procedures.

#### 7.2.5 Reactions/Side Effects to Condoms

Study staff will consult with an independent physician regarding the severity of any reactions or side effects to the study condoms. As appropriate, participants will be referred to AID Atlanta and study stopped.

### 7.2.6 Pregnancy

All participants who report that their current partner is pregnant or may be pregnant will be referred to the Grady Family Planning Wellness Clinic.

#### 7.2.7 Condom Failure Referrals

Participants who report condom slippage or breakage in electronic coital log entries will receive an email with resources for HIV and STI testing, plan B, and non-occupational post-exposure prophylaxis. An example email script is uploaded to eIRB.

#### 7.3 Measures

# 7.3.1 Visit Case Report Forms

Study staff will collect key data points using eCRFs at study visits. For the baseline visit, information to be collected on eCRF includes eligibility criteria, basic demographic information, and acute HIV and STI symptoms. For follow-up visits, eCRFs will include information regarding documentation of condition crossover, number of condoms distributed and returned, adverse events, and study stops.

#### 7.3.2 Baseline Survey

The baseline questionnaire will collect self-reported demographic information, information on prior HIV testing, information on history of condom use problems, information on substance use, and information on past sexual partners. Anticipated completion time is 30-45 minutes.

#### 7.3.3 Coital Log

Participants will be instructed to complete a mobile-optimized, web-based home coital log that can be securely loaded on personal devices (e.g. smart phones, tablets, personal computers). The coital log will first ask whether the participant has had sex since their last coital log entry. If the participant has had sex, the participant will record information on whether a condom was used, partner, lubricant use, type of sex, quality of erection, clinical condom performance, and event-level sexual pleasure.

#### 7.3.4 Outcome Measures

Pleasure, an outcome measure for Aim 1, will be measured at the event level through the coital log. Based on a literature search and consultation with experts, there is no extant event-level scale to assess pleasure. We therefore

- developed and validated a measure, based on a process that included a literature review to identify relevant constructs, an external expert scientific panel consultation to develop items and identify domains, and the conduct of a survey to validate the scale through determination of internal consistency, factor analysis, and correlational (construct) validity. The validated scale resulting from this process will be the measure we use to assess pleasure.
- Preference, an outcome measure for Aim 2, will be measured at the final study visit. For each combination of crossover conditions, there will be a paired comparison asking participants to select their preferred condom between the two relevant study conditions. We will also assess preference at interim study visits prior to beginning into the third crossover condition. For analysis purposes, we will use the final study visit data for preference if available, but for participants lost to follow-up we will use interim study visit preference responses.
- Total clinical condom failure, an outcome measure for Aims 3-4, will be measured at the event level through the coital log.
  - ISO guidance defines clinical failure as combined clinical breakage and slippage. 
    - "Clinical breakage as a condom failure event occurring when the condom breaks during intercourse or during withdrawal from the vagina.
    - Clinical slippage is defined as a condom failure event occurring when the condom slips completely off during intercourse or during withdrawal from the vagina.
    - Slippage occurring because the user failed to hold onto the condom at the base of the penis during withdrawal and/or because of delayed withdrawal are considered user failures and should be recorded as non-clinical slippage. (These user failures should not be counted as *clinical* slippage events).
    - o If a condom slips off primarily as a result of breakage, then it should not be counted as a slippage event.
    - If a condom both breaks and slips during a single used, then it is only counted as a single clinical failure."
  - As per ISO guidance specified above, condom slippage considered user error will not be considered clinical failure. Specifically, we will ask participants who experienced slippage on withdrawal whether (1) the participant held onto the base of the condom during withdrawal and (2) their penis was still hard when they pulled out of their partner's vagina/anus. Affirmative response to either of these questions will lead to the determination of user error and will not be considered to be clinical condom failure. For condom failure in which breakage and slippage occur, we will only count this as a single failure for calculation of total clinical failure rate.

28

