The daily coital log explored event-level questions that addressed the context of condom use and study outcomes; questions were based on items from ISO,[2] a cohort study of MSM,[3] and a validated pleasure scale[4]. Relevant to Aims 3 and 4, ISO guidance defines clinical failure as combined clinical breakage and slippage [2], and we will follow ISO guidance for calculating total clinical failure. For instance, any condom failure in which breakage and slippage occur for the same condom will be counted as a single failure for calculation of total clinical failure.

Based on a literature search and consultation with experts, we identified no extant event-level scale to assess pleasure. We therefore developed and validated the Event-level Male Sexual Pleasure Scale (EMSexPleasure), previously described elsewhere.[4] The coital log was used to assess study outcomes of Aim 1 pleasure (EMSexPleasure) and Aims 3/4 clinical failure for slippage/breakage (ISO). The log also assessed relevant context for the sexual act, with source of

item provided in parentheses: (a) Date and time of report (ISO), (b) whether a study condom, other condom, or no condom was used (ISO), (c) Partner name (cohort study), (d) Lubricant use (ISO), (e) Type of sex act (ISO), (f) failure outcome with condoms (ISO), and (g) Drug or alcohol use by participant (cohort study).

Endline measures

Preference, the outcome measure for Aim 2, was measured at the final study visit. For each of three possible combinations of two crossover conditions (standard/thin, thin/fitted, standard/fitted), there was a paired comparison asking participants to select their preferred condom between the two relevant study conditions. To maintain blinding, preference question response options were the color assigned to each of these condom types (e.g. blue or yellow).

References

2. International Organization for Standardization. *Condoms — Guidance on clinical studies — Part 1: Male condoms, clinical function studies based on self-reports*. 2012.

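### The user-error rule for slippage on withdrawal is inverted: as written it drops correct-use slips from clinical failure and counts double user-error slips in Aims 3 and 4

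*Protocol*

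**What the plan says.** Protocol section 7.3.4 (Outcome Measures) defines total clinical failure, the outcome for Aims 3 and 4, by quoting ISO guidance. On user error the quoted guidance covers "Slippage occurring because the user failed to hold onto the condom at the base of the penis during withdrawal and/or because of delayed withdrawal", and says of such events: "These user failures should not be counted as" clinical slippage.

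The same section then turns this into a scoring rule. It opens with the intent: "As per ISO guidance specified above, condom slippage considered user error will not be considered clinical failure". The rule applies to "participants who experienced slippage on withdrawal", who answer two yes/no items: did they hold the base of the condom, and were they still erect when they pulled out. The scoring is: "Affirmative response to either of these questions will lead to the determination of user error".

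Section 7.1.6 (Coital Log) words the items in the same direction: "whether they held onto the condom at the base of the penis while withdrawing, and whether the penis was still erect upon withdrawal".

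The SAP, under Coital log measures, says "we will follow ISO guidance for calculating total clinical failure". Its one example is that breakage and slippage of the same condom count once. It does not mention the two items or how they are scored.

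**The concern.** Holding on and still being erect are the correct-use answers. A man who says yes to both and still had the condom slip off has experienced product slippage, which is what clinical failure is meant to capture. The written rule calls this user error. A man who says no to both made both of the errors that the ISO text names, and the written rule calls this clinical failure.

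Total clinical failure is the outcome for two of the four primary aims (sections 9.0 and 9.4), and section 2 ties both to label indications. Aim 3 sets an absolute failure proportion for each condom against an FDA cut-point, so misclassified events move the estimate directly. Aim 4 compares fitted with standard condoms. Under the written rule, any benefit of fit on correct-use slippage at withdrawal cannot register at all, because those events never enter the outcome.

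**Working it through.** **Inputs.** The ISO text, the two items and the scoring rule come from Protocol section 7.3.4, and the direction of the log items from section 7.1.6. Section 7.1.2.5 (Participant Training) lists holding the rim on withdrawal among the eight steps of successful condom use, so a yes to the first item cannot denote an error. Treating loss of erection as the marker of delayed withdrawal is an inference, but it is how section 7.3.4 uses the item.

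**Step 1: the two rules as logic.**
- ISO as quoted: user error if not held or not erect. Clinical only if held and erect.
- Protocol rule: user error if held or erect. Clinical only if not held and not erect.

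| Held base | Still erect | ISO as quoted | Protocol rule | Agree? |
|---|---|---|---|---|
| Yes | Yes | Clinical failure | User error | No |
| Yes | No | User error | User error | Yes |
| No | Yes | User error | User error | Yes |
| No | No | User error | Clinical failure | No |

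Two of four patterns agree. The only pattern that ISO counts is never counted, and the only pattern that the protocol counts is one that ISO excludes. If a negative answer to either item is scored as user error instead, all four agree.

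**Step 2: possible effect on a failure rate.** The plan states no power or expected rate for Aims 3 and 4, so there is no figure of its own to reproduce. Let *r* be the true rate per act, *w* the share of true clinical failures that are yes/yes slips on withdrawal, and *u* the rate per act of no/no slips on withdrawal. Then

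recorded rate = *r* × (1 − *w*) + *u*.

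For *r* I use 6.3% and 6.9%, the two anal-sex failure rates cited in Protocol section 1. The documents do not say whether those studies excluded user error as ISO does, so they serve only as illustrations. Neither *w* nor *u* is given. I assume *w* = 10% to 50% and *u* = 0 to 2% per act.

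| *w* | *u* | *r* = 6.3% | *r* = 6.9% |
|---|---|---|---|
| 10% | 0 | 5.67% | 6.21% |
| 10% | 2% | 7.67% | 8.21% |
| 30% | 1% | 5.41% | 5.83% |
| 50% | 0 | 3.15% | 3.45% |
| 50% | 2% | 5.15% | 5.45% |

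For example, 6.9% × (1 − 0.50) + 0 = 3.45%, and 6.9% × (1 − 0.10) + 2% = 8.21%. The two errors cancel when *u* = *r* × *w*; at *r* = 6.9% and *w* = 30% that is 2.07% of acts. Below that value the recorded rate is too low, and above it too high.

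**Step 3: the Aim 4 contrast.** The formula applies to each condom with its own *w* and *u*. If these differ between fitted and standard condoms, the contrast changes by an amount and in a direction that the documents do not determine.

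**The case against.** The best defence is that this is a drafting slip, with affirmative written for negative. Section 7.3.4 declares that it follows ISO, and the SAP says the same without repeating the faulty sentence. Neither document shows the programmed derivation, so harm to the analysed data is not demonstrated. That stands: every consequence here is conditional on the rule being applied as written. It does not remove the fault. The SAP's general reference to ISO supplies no scoring of the two items, so a programmer must either follow the protocol and get the wrong outcome or depart from the protocol without written authority.

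Three limits on scope also stand. Breakage and slippage during intercourse are untouched. User error is wrongly counted only when both errors occur together; slips with a single error are scored correctly. And the net direction of the bias is unknown once no/no slips are included.

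Finally, it is an inference that fit should act mainly through slippage. The introduction links small size to looseness, but the only evidence by failure mode that it cites for fitted condoms concerns breakage, which this rule does not affect. The concern does not need that inference, because Aim 3 is exposed whatever the route of any fit effect.

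**Conclusion.** The concern holds. The scoring rule in section 7.3.4 contradicts the ISO definition quoted in the same section and misclassifies two of the four answer patterns for slippage on withdrawal. This follows from the protocol's own text and needs no outside source. It must be corrected, because it is the only operational rule for the outcome of two primary aims that support labelling.

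The size cannot be established. With *w* of 10% to 50% and *u* of 0 to 2%, both assumed, a true 6.3% would be recorded as 3.15% to 7.67%, and a true 6.9% as 3.45% to 8.21%. Whether the analysed data are affected depends on which rule was programmed.

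**What to change.** Replace the scoring sentence in section 7.3.4 with: *A negative response to either question (did not hold the base of the condom, or penis no longer hard) will be classed as user error (non-clinical slippage). Slippage on withdrawal counts as clinical failure only if both responses are affirmative.*

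Put the same rule in the SAP as an explicit derivation of total clinical failure, naming both coital-log items. Check the derivation program against the four-row table above. If the inverted rule was programmed, re-derive the outcome and rerun Aims 3 and 4.

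The cost is one sentence in each document and a code check. No new data are needed, since the coital log already collects both items.

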## 7.4 Training

All study recruiters will complete a two-hour training on recruitment procedures and use of study screening instruments.

All study staff, including recruiters, counselors, phlebotomists, and others involved with research events will complete CITI training regarding biomedical and social/behavioral ethics in study operations and data management and good clinical practice. All study staff involved in the handling of biological specimens will be trained in Biohazard Safety (Emory University Environmental Health and Safety Office courses Research Laboratory Safety, Biosafety, and Bloodborne Pathogens for Research). All study staff who will be conducting HIV testing or phlebotomy will have certification of Hepatitis B immunization and titer. Study staff who have contact with blinded participants will be trained in how to interact with blinded participants.

All study staff who conduct HIV counseling and testing will complete a three-day training in HIV prevention counseling and rapid testing, according to the CDC training curriculum. All HIV counselors and testers will complete at least 40 hours of supervised HIV counseling and testing experience prior to independent counseling.

Those performing phlebotomy will have training in phlebotomy and will have at least 40 hours of experience drawing blood as a phlebotomist or registered nurse.

### 8. SAFETY MONITORING AND ADVERSE EVENT REPORTING

# **8.0 Safety Monitoring**

To minimize risks and ensure the safety of subjects, at study visits study staff will refer to participants by their initials, not their names and keep all participant materials locked in a secure location. All electronic data will be stored in a secure environment hosted by Dacima, and copies of the dataset will be downloaded to a securely segregated SQL table on the secure (Health Insurance Portability and Accountability Act (HIPAA) Compliant) server at the Emory University Rollins School of Public Health. Any hard copy data will be secured in a locked office and locked filing cabinet.

The principal investigator has developed a data and safety monitoring plan (uploaded to eIRB). The principal investigator will monitor data collection throughout the study, and will ensure that interview protocols are followed, all adverse event reports are reviewed (if any), confidentiality procedures are implemented, and the Emory University IRB is alerted if unexpected concerns arise.

The project team will meet regularly to discuss progress toward data collection goals. At these meetings, study staff will prepare weekly reports on data collection and any emerging issues or potential problems regarding the data collection efforts. The following will be reported by the principal investigator in writing to the Emory University IRB: all serious adverse events associated with the study procedures and/or any incidents or problems involving the conduct of the study staff or subject participation, including problems with the consent processes.

## 8.1 Adverse Event Definitions and Reporting Requirements

#### **8.1.1** Adverse Events Definitions

### 8.1.1.1 Adverse Events

An AE is defined as any unfavorable or unintended sign (including laboratory findings), symptom or disease that occurs to a subject while enrolled in a clinical trial that could be associated with the use of the study intervention. Medical conditions that exist at study enrollment are not considered an AE unless condition worsens after use of the study intervention.

In this study, the study intervention includes provision of condoms, lubricant, and HIV testing and counseling. Possible adverse events for all participants include symptomatic STI infection, acute HIV infection, discomfort or other issues related to the study condoms, and pregnancy (for current partner of MSW).

